6 TREATMENT PLAN

6.1 Administration Schedule

6.1.1 Treatment Arm 1

After randomization at Visit 2, participants of the Treatment Arm 1 will be initiated on Amitriptyline 25 mg daily (to be taken at bedtime) for two weeks during the "Titration Period". Starting at Study Week 5, the amitriptyline dose will be titrated up to 50 mg (two capsules of amitriptyline 25 mg) when entering the "Intervention Period". For those participants who report intolerance to the 50 mg dose due to the adverse effect, the dose will be tapered down to 25 mg dose for three to five days, before another trial for the 50 mg dose. For those who still do not tolerate amitriptyline 50 mg, they will be asked to continue the 25 mg dose for the rest of the Intervention Period.

At the end of the Intervention Period, the participants who take amitriptyline 50 mg will be reduced to amitriptyline 25 mg daily for another one to two weeks ("Taper Period"), and discontinue the 25 mg daily dose as tolerated. For the participants who are taking amitriptyline 25 mg at the end of the Intervention Period, they will discontinue treatment with the study drug at that time.

6.1.2 Treatment Arm 2

After randomization at Visit 2, participants of the Treatment Arm 2 will be initiated on the matching placebo of Amitriptyline 25 mg daily (to be taken at bedtime) for two weeks during the "Titration Period". Starting at Study Week 5, the matching placebo of amitriptyline 50 mg (two capsules of matching placebo of amitriptyline 25 mg) will be initiated when entering the "Intervention Period". For those participants who report intolerance to the matching placebo of amitriptyline 50 mg dose due to the adverse effect, the matching placebo will be switched back to that of the amitriptyline 25 mg for three to five days, before another trial for the matching placebo for amitriptyline 50 mg. For those who still do not tolerate the matching placebo for amitriptyline 50 mg, they will be asked to continue the matching placebo of amitriptyline 25 mg dose for the rest of the Intervention Period.

At the end of the Intervention Period, the participants who take the matching placebo of amitriptyline 50 mg will be asked to take the matching placebo of amitriptyline 25 mg for another one to two weeks ("Taper Period"), and discontinue the matching placebo as tolerated. For the participants who are taking matching placebo of amitriptyline 25 mg at the end of the Intervention Period, they will discontinue treatment with the study drug at that time.

6.2 Treatment (include name of each treatment as section header)

6.2.1 How Supplied, Stored, Packaged and Labeled

Amitriptyline 25 mg: Over-encapsulated for blinding.

Matching placebo capsules: Capsules identical to the ones used to encapsulate amitriptyline for blinding.

Store at 20° to 25°C (68° to 77°F); excursions permitted to 15° to 30°C (59° to 86°F) (See USP Controlled Room Temperature). Dispense in a tight, light-resistant container.

6.2.2 Preparation and Administration

At Visit 2, participants will be given a 10-week supply of amitriptyline sufficient for 2 weeks of 25 mg daily and 8 weeks of 50 mg (i.e., two capsules of 25 mg) daily. At Visit 3, the participants will then be given a 2-week supply of amitriptyline 25 mg, if needed.

The matching placebo will be provided in a similar fashion.

6.2.3 Accountability and Compliance

Participants will be asked to return medication bottles and any unused study drugs at the end of the Interventional Periods (i.e., Visit 3) for reconciliation. For participants who will require amitriptyline 25 mg or matching placebo for the Taper Periods, Guide of Safe Medicine Disposal following the FDA and Utah State regulations, including returning the unused study drugs to the study team, will be provided.

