4 STUDY DESIGN

4.1 Description

The current investigation is a pilot phase II clinical trial with placebo control, randomization and double-blinding design.

After the initial recruitment (Visit 1), the study participants will enter a two-week "Runin Period", during which the participants will be asked to continue their CGM use and record their symptom(s) on Hypoglycemic Event Reports for all their hypoglycemic events. For the participants who meet the criteria to be initiated on study drug (see recruitment criteria), they will then be randomized to be initiated either on daily amitriptyline or a matching placebo (Visit 2). All participants will undergo a two-week drug "Titration Period", and at the end of this period (i.e., the end of Week 4), the amitriptyline dose will be titrated up with a matching placebo and continued until Visit 4. During this "Intervention Period", the patient will receive telephone follow-ups at Week 5 and Week 7, and undergo a return visit (Visit 3). After Visit 3, the participants will again start to record their hypoglycemic symptoms, and then return to Visit 4 at the end of the Intervention Period. The participants will then undergo a two-week study drug "Tapering Period" to complete the study drug intervention. At week 27 and 39 of the study, the participants will be assessed with follow-up questionnaires.

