6.3 Duration of Therapy

The total duration of the treatment period will last about 12 weeks.

Subjects must be withdrawn or discontinued from the clinical trial for the following reasons:

- Subject withdraws consent from participation in the clinical trial. A subject must be removed from the study at his/her own request or at the request of their legally authorized representative. At any time during the trial and without providing reasons, a subject may decline to participate further. The subject will not suffer any disadvantage as a result.
- Subject is lost to follow-up despite efforts to contact
- Death

Subjects may be withdrawn or discontinued from the clinical trial for the following reasons:

- The subject is non-compliant with study treatment requirements and/or protocol procedures, including the use of prohibited concomitant medications.
- The occurrence of an AE, laboratory abnormality, or other medical condition or situation such that in the investigator's opinion, continued participation in the study would not be in the best interest of the subject.

Discontinued or withdrawn subjects may be replaced for each treatment arm.

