9.10.1 Primary Objective Assessment

The primary objective assessment will be done through the determining areaunder-curve for CGM glucose level < 70/54 mg/dL and the total and recognized hypoglycemic episodes based on CGM data and hypoglycemic event reports, respectively.

A single CGM hypoglycemic episode will be defined by any CGM readings < 70 mg/dL lasting equal to or more than 20 minutes on the CGM data.

A participant will complete a hypoglycemic event report for all hypoglycemic events during the surveillance periods. A hypoglycemic event report will include information about whether the participants perceive symptom(s) for hypoglycemic episodes recorded based on CGM.

At each visits, CGM data will be downloaded into a secure system and exported into an Excel format, and the hypoglycemic event reports will be prepared for analysis.

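### Section 6.2.3 labels Visit 3 (Week 11) as the end of the Intervention Period for drug return; the rest of the protocol puts it at Visit 4 (Week 13)

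*Combined protocol and SAP*

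**What the plan says.** Section 6.2.3 (Accountability and Compliance) asks participants to "return medication bottles and any unused study drugs at the end of the Interventional Periods (i.e., Visit 3) for reconciliation". Its next sentence deals separately with participants who need 25 mg or matching placebo for the taper.

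Section 4.1 (Description) places the end elsewhere. After titration, "the amitriptyline dose will be titrated up with a matching placebo and continued until Visit 4". Visit 3 is a return visit within the Intervention Period. After it, "the participants will again start to record their hypoglycemic symptoms, and then return to Visit 4 at the end of the Intervention Period".

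Section 6.2.2 provides at Visit 2 a "10-week supply of amitriptyline sufficient for 2 weeks of 25 mg daily and 8 weeks of 50 mg" daily, the 50 mg dose being two 25 mg capsules. It then adds: "At Visit 3, the participants will then be given a 2-week supply of amitriptyline 25 mg, if needed". Section 6.3 states: "The total duration of the treatment period will last about 12 weeks".

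The study calendar (Section 8) puts Visits 2, 3 and 4 at Weeks 3, 11 and 13, and marks investigational drug treatment at both Visit 3 and Visit 4.

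On symptom recording, Section 4.1 describes the run-in as a period "during which the participants will be asked to continue their CGM use and record their symptom(s) on Hypoglycemic Event Reports", and recording restarts only after Visit 3. Section 9.10.1 says: "A participant will complete a hypoglycemic event report for all hypoglycemic events during the surveillance periods". It does not define those periods by visit.

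**The concern.** Sections 4.1 and 6.2.3 cannot both be followed. If drug is collected at Visit 3, the assigned dose cannot continue to Visit 4 from the supply that was issued for that purpose.

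The timing makes this worth correcting. Section 9.10.1 takes recognized episodes from the event reports, and Section 10 names the recognized-to-total ratio as the outcome for the exact Wilcoxon test. On Section 4.1's account, event reports are kept in the run-in and again only between Visits 3 and 4. The fortnight in which the misplaced return would remove the drug is therefore the one that supplies the post-baseline value of that ratio.

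Section 6.2 does not show its own error. Read alone, Sections 6.2.2 and 6.2.3 describe a sequence that hangs together: collect what is left at Visit 3, then hand over two weeks of 25 mg capsules. Staff working from those paragraphs would have no signal that the visit number is wrong.

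Adherence is a second, smaller matter. Section 6.2.3 specifies no other reconciliation for the Intervention Period, Section 3 rules out plasma-level monitoring, and the calls that remind participants about adherence fall at Weeks 5 and 7. A count taken at Visit 3 therefore says nothing about the fortnight that follows, even if staff hand the capsules back.

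**Working it through.** The check is calendar and capsule arithmetic. It assumes 25 mg capsules counted from the stated regimen (Section 6.2.2 gives a duration, not a count), full adherence, and nominal visit dates unless noted.

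**Inputs**
- Visit 2 at Week 3, Visit 3 at Week 11, Visit 4 at Week 13 (Section 8).
- One capsule daily for 2 weeks, then two capsules daily from Week 5 (Sections 6.1.1 and 6.2.2).
- Taper of one to two weeks at 25 mg after the Intervention Period (Section 6.1.1).
- Visit window of plus or minus 3 days (Section 8, note 4).

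**1. Reproduce the 10-week supply.** Visit 2 to Visit 4 is 13 − 3 = 10 weeks, or 70 days: 2 weeks of titration plus 8 weeks at 50 mg. In capsules, 14 × 1 + 56 × 2 = 126. The supply runs exactly to Visit 4. Visit 2 to Visit 3 is only 11 − 3 = 8 weeks, or 56 days.

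**2. Reproduce the total duration.** Ending at Visit 4 with the full taper gives 10 + 2 = 12 weeks, which matches Section 6.3. Ending at Visit 3 gives 8 + 2 = 10 weeks, which does not.

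**3. Capsules in hand at Visit 3 on 50 mg.** Used: 14 + 42 × 2 = 98. Left: 126 − 98 = 28. Needed from Visit 3 to Visit 4: 14 × 2 = 28. The amount to be returned is the amount still required. If Visit 3 moves by 3 days and other dates hold:
- Early: 53 days elapsed, 14 + 39 × 2 = 92 used, 34 left.
- Late: 59 days elapsed, 14 + 45 × 2 = 104 used, 22 left.

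**4. Coverage of the pill count.** At Visit 3 it covers 56 / 70 = 80% of intervention days and 0 of the 14 days in the event-report window. At Visit 4 it covers 70 of 70.

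**5. After the correction.** At Visit 4 the same participant has used 14 + 56 × 2 = 126 of 126, so no planned capsules remain and the count reconciles the whole period.

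The counts in steps 3 and 5 are for a participant who stays on 50 mg. No claim is made about participants held at 25 mg.

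**The case against.** The strongest reply is that this is a slip in a parenthesis. The words just before it, which tie return to the end of the intervention, are right; only the visit number is wrong. Section 4.1 gives the correct visit, the calendar marks drug treatment at Visits 3 and 4, and Section 9.10 has dosing follow the assessments on treatment visit days. A careful coordinator would probably notice. This stands, and it is why the point is minor. It does not remove the case for correcting an instruction that staff carry out.

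A second reply is that the 25 mg supply issued at Visit 3 is evidently taper stock. Two weeks at 25 mg matches the longest taper, and issuing it only where needed fits Section 6.1.1, under which participants on 25 mg stop without a taper. This also stands. A reader might infer that participants would live on those capsules between Visits 3 and 4 and so receive some calculable fraction of the assigned dose. No section instructs that use, so no such fraction is put forward.

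Third, Section 10 names no analysis that uses pill counts, and Section 6.2.3 allows unused taper drug to come back to the study team. The loss of adherence information is real, but its analytic weight is small.

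Fourth, Section 9.10.1 leaves the surveillance periods undefined, and the calendar marks a primary objective assessment at Visit 3 as well. That Visits 3 to 4 form the only post-baseline event-report window is therefore an inference from Section 4.1, not an express statement.

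**Conclusion.** The visit number in Section 6.2.3 is wrong as written. Section 4.1 says so expressly, and the calendar, the Visit 2 supply and the total duration fit only Visit 4. If the rule is followed literally, a fully adherent 50 mg participant returns the 28 capsules needed for Weeks 11 to 13 at nominal timing, and the count misses 14 of 70 intervention days, the same 14 in which event reports are inferred to be kept. The severity is minor: the harm depends on the literal reading, and the intent is recoverable.

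Three stronger conclusions are tempting, and the documents support none of them.
- A reader might infer that the treatment comparison on the ratio will be biased. Nothing shows that sites will act on the wrong number, and the documents give no dose-response data, so no effect on the ratio can be estimated.
- A reader might infer that the CGM area-under-curve outcomes escape because CGM data are collected at all four visits. Sections 9.10.1 and 9.10.2 describe data collection but do not define the window analysed, so the exposure of those outcomes cannot be judged either way.
- A reader might infer that the Visit 2 supply is too small if Visit 4 runs late. That is a separate question. Section 6.2.2 does not exclude overage, and note 4 of the calendar does not say whether later dates are reset from the actual Visit 2.

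**What to change.** In Section 6.2.3, change Visit 3 to Visit 4 for return and reconciliation, and add a sentence that participants keep the Visit 2 supply and stay on their assigned dose until Visit 4. In Section 6.2.2, state that the 25 mg supply issued at Visit 3, and its matching placebo, is taper stock for use after Visit 4.

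The cost is one visit number and two short clarifications. This correction adds no visit, capsules or analysis.

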6.3 Duration of Therapy

The total duration of the treatment period will last about 12 weeks.

Subjects must be withdrawn or discontinued from the clinical trial for the following reasons:

- Subject withdraws consent from participation in the clinical trial. A subject must be removed from the study at his/her own request or at the request of their legally authorized representative. At any time during the trial and without providing reasons, a subject may decline to participate further. The subject will not suffer any disadvantage as a result.
- Subject is lost to follow-up despite efforts to contact
- Death

Subjects may be withdrawn or discontinued from the clinical trial for the following reasons:

- The subject is non-compliant with study treatment requirements and/or protocol procedures, including the use of prohibited concomitant medications.
- The occurrence of an AE, laboratory abnormality, or other medical condition or situation such that in the investigator's opinion, continued participation in the study would not be in the best interest of the subject.

Discontinued or withdrawn subjects may be replaced for each treatment arm.

7 TOXICITIES AND DOSE MODIFICATION

Toxicities will be monitored in each study subject according to the study calendar and Section 9.11, Safety Measurements. Serious Adverse Events and intolerable toxicities determined by the PI to be related to study medication will result in discontinuation of treatment and withdrawal of the subject from the trial. Treatment may be reduced and resumed if adverse events resolve to a tolerable level as determined by the investigator.

This study will utilize the CTCAE (NCI Common Terminology Criteria for Adverse Events) version 4.0 for adverse event and serious adverse event reporting.

7.1 Dose Modification

For those participants who report intolerance to the 25 mg dose due to the adverse effect, the amitriptyline will be stopped for three to five days before another trial. Similarly, for those participants who report intolerance to the 50 mg dose after up-titration from 25 mg, the dose will be tapered down to 25 mg dose for three to five days, before another trial for the 50 mg dose. For those who still do not tolerate amitriptyline 50 mg, they will be asked to continue the 25 mg dose for the rest of the Intervention Period.

7.2 Supportive Care

All supportive measures consistent with optimal subject care will be given throughout the study.

8 STUDY CALENDAR

| Period | Screening ¹ /Run-in | | Т | Follow-up | | | | |
|---|-----------------------------------|------------------|----|-----------|----------------|----------------|----|----|
| Visit No. | 1 | 2 | _2 | _2 | 3 | 4 | _3 | _3 |
| Week ⁴ | -4 to 1 | 3 | 5 | 7 | 11 | 13 | 27 | 39 |
| Assessments | | | | | | | | |
| Informed consent | Х | | | | | | | |
| Inclusion/Exclusion criteria | Х | | | | | | | |
| Demographics | Х | | | | | | | |
| Vital signs | Х | Х | | | Х | Х | | |
| Physical Examination | Х | X ⁵ | | | X ⁵ | X ⁵ | | |
| Pregnancy Test | Х | Х | | | | | | |
| ECG | | \mathbf{X}^{1} | | | | | | |
| Comprehensive Metabolic Panel ⁶ | Х | | | | | | | |
| HbA1c | | Х | | | | Х | | |
| AE Assessment | | Х | Х | Х | Х | Х | | |
| Concomitant Medications | Х | Х | | | Х | Х | | |
| Investigational Drug Treatment | | Х | Х | Х | X | X | | |
| Primary Objective Assessment | X ⁷ | X | | | X | X | | |
| Secondary Objective Assessment | X ⁷ | Х | | | X | X | X | X |

- 1. All screening procedures should be completed within 4 weeks of study enrollment, except that an ECG and laboratory evaluation completed within 3 months will be considered as valid.
- 2. Telephone call follow-up to assess participants' adverse events, and to remind study drug titration/adherence.
- 3. Telephone call follow-up to assess participants' general well-being, and to complete questionnaire surveys for Secondary Objective Assessment.
- 4. All visits/telephone calls can occur within +/- 3 days of the anticipated dates based on the schedule calendar
- 5. Follow-up physical exam to be conducted at the discretion of PI/Sub-investigator based on reported adverse events.
- 6. Comprehensive Metabolic penal include Albumin, Alkaline Phosphatase, Aspartate Aminotransferase, Alanine Aminotransferase, Total Bilirubin, Calcium, Carbon Dioxide, Creatinine, Chloride, Glucose, Potassium, Protein, Sodium and Urea Nitrogen.
- 7. Including instructions about Hypoglycemic Event Reports and conducting questionnaires surveys to assess baseline status. Will only be provided only after obtaining the consent.

9 STUDY PROCEDURES

Detailed descriptions of subject evaluations required for this protocol are described in this section. These evaluations will be performed during the indicated visits/weeks of the study as described in the Study Calendar and in this section.

All data collected are to be recorded on source documents and entered into the appropriate CRF page.

The PI is responsible for maintaining a record of all subjects pre-screened, screened, and enrolled into the study. All subjects must provide written informed consent before the performance of any study procedures.

9.1 Participant Identification/Recruitment Process

Describe the recruitment/participant identification process in detail (e.g. who will review charts or records, who can refer participants to the study, where will flyers be posted, how often will recruitment letters be sent, when will follow-up phone calls be made, etc.):

2) Study flyers which include the study survey web link/address will be printed. These printed study flyers will be placed in patient encounter rooms of the University of Utah Endocrinology clinics. The study flyers will also be placed/distributed at the front desk for interested patients. Information about the current study will be distributed to clinical providers, including University of Utah Endocrinologists and diabetes educators.

3) The study investigator(s) and coordinator(s) may approach the potential candidates after visits for clinical and research purposes and to discuss with potential candidates about the current research opportunity.

For each recruitment route, the candidates may "optout" for no further contact to be made for this study. On the myChart message/email/mail/flyer/study survey, contact information will be provided for candidates' inquiries.

The PI will work with the University of Utah Enterprise Data Warehouse (EDW) for initial candidate screening with based on the elements of inclusion/exclusion criteria (e.g. type 1 diabetes, age, recent HbA1c, etc) on the Human Subject Recruitment tool. The Human Subject Recruitment tool is a computer software managed by the EDW for subject recruitment with a constantly updating database, and this tool is commonly utilized for clinical investigations at the University of Utah. The study team will then review of these candidates' medical charts for further candidate selection. The study team will also review the medical charts of the patients with recent/upcoming visits scheduled with University of Utah Endocrinology Clinics for potential candidates screening. A list of potential candidates will be generated and used to recruit subjects in the following routes:

1) Care providers (including primary care physicians, Endocrinologists or Diabetes Educators) with established clinical relationships with the potential candidates may discuss the research opportunity with the candidates, to obtain the permission of contact for interested candidates, and/or offer recruitment letters.

2) A recruitment letter may be sent via mail or email or myChart message to the potential candidates. If no response is received in at least 7 days after the mail/message being sent, a phone call may be generated to discuss the study.

3) A research assistant/coordinator may present at the University of Utah Clinics to discuss with the potential candidates. Communication with the care providers will be done before the research assistant/coordinator approaches the potential candidates.

Other recruitment methods include the following:

- 1) Study flyers will be placed in patient encounter rooms, phlebotomy site and the front desk at the Endocrinology Clinics.
- 2) Information about the current study will also be distributed to clinicians, mostly primary care physicians and endocrinologists, and referrals for the current study may be made by these physicians.

For each recruitment route, the candidate may opt-out request for no further contact to be made for this study.

For interested candidates, we will proceed with further eligibility screening through telephone discussions and mailing/emailing surveillance of Personal Medical History and other questionnaires. A copy of the consent form will also be mailed/emailed to the candidates to look over for at least 1 day before obtaining consent.

